
#### Statistical evaluation of study aims

#### Aim 1. Compare the effectiveness of menthol versus tobacco EC at facilitating switching at week

**12. Primary hypothesis.** *Participants randomized to tobacco EC (versus menthol EC) will demonstrate non-inferior rates of complete and predominant switching to EC (primary outcome). Complete switching is defined as exclusive use of EC, biochemically confirmed with CO < 6 ppm, and predominant switching is defined as use of EC with > 50% reduction in CPD.* We will test this hypothesis by calculating the 95% confidence interval for the difference in P1-P2, as defined above. To show noninferiority the upper limit of the confidence interval must be greater than or equal to 0.00 and lower limit of the confidence interval must be larger than -0.09. If the upper limit of the confidence interval is less than 0.00 then we cannot conclude noninferiority. If the upper limit is greater than or equal to 0.00 and the lower limit is less than or equal to -0.09 then the results would be inconclusive.

Rates of complete and predominant switching will also be compared separately by group using the chisquare test. Note, that we have not specified an a priori difference threshold for these analyses and, therefore, they are not testing noninferiority and should be considered exploratory. What these analyses will provide is an estimate of the proportion of complete switchers in the tobacco EC versus menthol EC group and, separately, an estimate of the proportion of predominant switchers in the tobacco EC versus menthol EC group.

Aim 2. Compare tobacco harm reduction of menthol versus tobacco EC at week 12. Hypothesis 2. Participants randomized to tobacco EC (versus menthol EC) will demonstrate comparable (i.e., no statistically significant differences) change in CO, respiratory symptoms, lung function, blood pressure, and tobacco-related quality of life from baseline to week 12. Each of these measures are on a quantitative scale and, given the sample size, we can assume the central limit theorem will hold. Thus, we will calculate the mean change and standard deviation of the change for each of these measures from baseline to week 12 by group. We will then conduct the two-sample t-test comparing the means between the groups while also reporting the corresponding 95% confidence intervals. Given that we expect to show noninferiority and comparable effects between groups, we except to fail to reject each of these tests and thus each confidence interval for the difference between groups will contain 0.00. However, if any of these variables are different when noninferiority is seen – i.e., Aim 1 is supported, meaning tobacco EC are found to be non-inferior to menthol EC on rate of switching - we will then utilize logistic regression analyzes to identify any phenotypic or consumption patterns that may predict why these variables differ in the face of noninferiority. For example, we may find that tobacco-related quality of life differs by group even though tobacco EC were found to be noninferior to menthol EC on rate of switching. In this case, factors such as gender, age, socioeconomic status, study-related side effects, adverse events, change in CPD, cigarette-related withdrawal, craving, dependence, EC usage and grams of e-liquid consumed, subjective effects of vaping, baseline smoking history, or psychosocial factors may explain this difference and the regression analyses undertaken will illuminate the potential reasons for the difference. If noninferiority is not seen - i.e., Aim 1 is not supported -- then we expect to see a difference in one or more of these measures.

Aim 3. Compare the acceptability of menthol versus tobacco EC at week 12. Hypothesis 3.

Participants randomized to tobacco EC (versus menthol EC) will consume comparable amounts of study provided e-liquid (measured in grams) and demonstrate comparable reductions in cigarette-related withdrawal, craving, and dependence. Subjective effects of vaping will also be compared between groups. Each of these measures are on a quantitative scale and, given the sample size, we can assume the central limit theorem will hold. Thus, we will calculate the mean e-liquid consumption over 12 weeks and its corresponding standard deviation by group. We will then compare the difference in these means between the groups using a two-sample t-test and calculate the corresponding 95% confidence interval. Given that we expect to show noninferiority in tobacco EC versus menthol EC, we expect to find no difference in e-liquid consumption and, therefore, the confidence interval for the difference between groups will contain 0.00. If noninferiority is not seen, then we may see a difference in the e-liquid consumption by group. For change in cigarette-related withdrawal, craving, dependence, and subjective effects of vaping, we will calculate the mean change and corresponding standard deviation for each of these measures by group. We will then conduct the two-sample t-test comparing the means between the groups while also reporting the corresponding 95% confidence intervals. Given that we expect to show noninferiority in tobacco EC versus menthol EC, we expect to find no difference in cigarette-related withdrawal, craving, dependence, or subjective effects of vaping. This means that we expect to fail to reject each of the t-tests and expect that each confidence interval for the difference between groups will contain 0.00. However, as described in Aim 2, if any of these variables are different when noninferiority is seen, we will then utilize logistic regression to identify any phenotypic or consumption patterns – e.g., gender, age, socioeconomic status, study-related side effects, adverse events, change in CPD, cigarette-related withdrawal, craving, dependence, EC usage and grams of e-liquid consumed, subjective effects of vaping, baseline smoking history, or psychosocial factors -- may explain this difference and the regression analyses undertaken will illuminate reasons for the difference.

If noninferiority is not seen, then we would expect to see a difference in one or more of these measures.

**Aim 4. Examine the long-term effectiveness of menthol versus tobacco EC at week 26.** We will compare switching patterns at week 26 to examine long-term maintenance of EC and smoking patterns under naturalistic conditions (EC only provided up to week 12). **Hypothesis 4.** *There will be no statistically significant difference in rates of complete or predominant switching at week 26 between those randomized to menthol versus tobacco EC.* For this aim we will calculate the proportion of complete and predominant switchers as defined above but at week 26. We will then calculate the corresponding 95% confidence interval on the difference in these proportions. The lost to follow-up rate at month 6 in the RCT that forms the basis for this proposal was < 10%. We do not expect the lost to follow-up rate to exceed 20% at month 6; however, given that we are not sure of our loss to follow-up rate we will report complete and

predominant switching at month 6 assuming those lost are not complete or predominant switchers and subsequently report on completers only.

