versus tobacco EC at facilitating switching from tobacco cigarettes to EC in adult menthol smokers transitioning to EC. We anticipate enrolling > 80% racial/ethnic minorities (primarily AA and Latinx) into the current study, thereby focusing on the populations who will be most impacted by regulatory action on menthol.

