#### C. Sample size, statistical methods, and power calculation

Sample size calculation. The aim of this non-inferiority trial is to establish that tobacco EC are not inferior to menthol EC in terms of the primary outcome, which is the proportion of menthol smokers who make a complete or predominant switch to EC, defined as use of EC along with a > 50% reduction in cigarettes from baseline to week 12. We assume 1) based on our RCT, that 73% in the menthol EC group will be complete or predominant switchers at week 12. We arrived at the 73% estimate at week 12 by examining the trend in switching from week 2 to week 6 in our RCT. Specifically, we noted a 12% reduction in switching from week 2 to week 6 and assumed that a similar trend would continue through week 12. Given an 85% switch rate in the menthol EC group at week 6 in our RCT and assuming a 12% reduction in switching from week 6 to 12, gives us a 73% switch rate at week 12. We also assume 2) to prove non-inferiority, the proportion in the tobacco EC group that are complete and partial switchers at week 12 will be similar to the menthol EC as long as it is greater than 64%. So, we can assume that P1=the proportion in the tobacco EC group that will be complete or predominant switchers at week 12=0.64 and that P2= the proportion in the menthol EC group that will be complete or predominant switchers at week 12=0.73. Then to test for noninferiority we have the following hypotheses: H0 (null hypothesis): P1-P2  $\leq$  -0.09 and H1 (alternative hypothesis): P1-P2 > -0.09. Following these assumptions 400 per group gives us 82% power with a Type 1 error rate of 2.5% using a normal approximation test for non-inferiority. Sample size calculations were done with PASS 16.0.4. **Basis for sample size calculations.** Estimates for non-inferiority trials are guided by an effectiveness ratio that indicates how effective one product is relative to another product and is determined from estimates on the outcome of interest and the a priori difference threshold. The FDA and other regulatory bodies have established an effectiveness ratio of  $\geq$  80% to indicate bioequivalence (i.e., non-inferiority). This is the criterion that we used in determining sample size for this study. Recent tobacco non-inferiority studies, including a tobacco harm reduction study comparing EC to heat-not-burn, have used a difference threshold of 15%.  Using this 15% threshold and our estimate of a 73% complete or predominant switch rate in the menthol EC group gives us an effectiveness ratio of 79% (.58/.73), which is under the criteria set by FDA. Raising the difference threshold to 14% would give us an effectiveness ratio of 81% (.59/.73). While this meets FDA criteria for non-inferiority, we felt that a difference of 14% was too large. Rather, we have gone with a more stringent difference threshold of 9%; at this threshold the proposed effectiveness ratio for our study is 88% (.64/.73), meaning that tobacco EC will be assumed to not be inferior to menthol EC if they are at least 88% as effective at facilitating a complete or predominant switch as menthol EC. This criterion places us well above the equivalence threshold set by the FDA and is more conservative than similar tobacco harm reduction non-inferiority studies, which we believe is a strength of this study. Missing **data.** We expect minimal (<5%) lost to follow-up at week 12 based on our recent studies, however those lost will be considered as non-complete or predominant switcher and will be imputed as such.

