#### **Treatment Overview.**

**Randomization.** All eligible participants who provide written informed consent and complete the baseline survey will be stratified by race and gender and randomized 1:1 to either menthol or Virginia tobacco EC. Randomization will be determined by computer-generated random numbers. Randomization assignments will be placed in sealed envelopes with sequential study ID numbers. After baseline data collection has been completed, the research assistant will select the sequential study ID number to determine the randomization assignment.

**EC (Weeks 0-12).** Participants will be provided a 12-week supply of VUSE 5% nicotine concentration in either menthol or Virginia tobacco that will be dispensed at the weeks 0, 4, and 8 in-person visits (4-week supply @ each visit). One pod delivers the equivalent of one pack of cigarettes, with variability of 13-30 cigarettes based on user,  and therefore allocation will be based on 1 pod per pack of cigarettes at week 0 and on current use patterns at weeks 4 and 8.

**EC use.** Participants will be instructed to use only the study EC in the flavor provided but to report all ECs by timeline follow-back at follow-up visits. To aid in recall and assessment of fidelity to protocol, participants will be given dated bags to collect all EC. Bags will be returned at each visit during the intervention phase to confirm use of EC (i.e., grams of e-liquid consumed and count of pods) as well as protocol adherence (i.e., the number of pods/grams vaped in the study provided versus non-study provided flavor) (see Measures). Those not attending EC dispensing visits will be reached by phone and delivered enough to get them to the next dispensing time point. Participants will be compensated for returned pods, but earnings will not be tied to protocol adherence. Participants will be paid for returned pods even if they return non-study provided EC to increase honest reporting.

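### Race and gender stratify the randomization but enter no planned between-group comparison, and Aims 2 and 3 do not adjust for baseline, so the intervals are valid but wider than they need to be

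*Combined protocol and SAP*

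**What the plan says.** Section II.E (Treatment Overview, Randomization) says that eligible participants "will be stratified by race and gender and randomized 1:1 to either menthol or Virginia tobacco EC". Section II.C then sets out the analyses.

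- **Aim 1 (primary):** "We will test this hypothesis by calculating the 95% confidence interval for the difference in P1-P2, as defined above". The lower limit is compared with -0.09. Complete and predominant switching are also compared separately by chi-square test. No strata or covariates are named.
- **Aim 2:** mean change from baseline to week 12 by arm, then "We will then conduct the two-sample t-test comparing the means between the groups". The expectation is that each test fails to reject and "thus each confidence interval for the difference between groups will contain 0.00".
- **Aim 3:** a t-test on mean e-liquid grams over 12 weeks. The other measures use change scores: "For change in cigarette-related withdrawal, craving, dependence, and subjective effects of vaping, we will calculate the mean change". These are again compared by t-test and read against zero.
- **Aim 4:** a 95% interval for the difference in proportions at week 26.
- **Contingent models (Aims 2 and 3):** if non-inferiority is shown but a measure differs, "we will then utilize logistic regression analyzes to identify any phenotypic or consumption patterns that may predict why these variables differ".

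On sample size, Section II.C states that "400 per group gives us 82% power with a Type 1 error rate of 2.5" percent.

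**The concern.** Stratifying the allocation implies that race and gender are expected to matter for outcome. If they do, ignoring them in the analysis leaves their variance in the standard error. In Aims 2 and 3 the baseline value enters only by subtraction. That is less efficient than using it as a covariate unless the regression slope of week 12 on baseline happens to equal 1.

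For Aim 1 this cannot create a false non-inferiority claim; it only gives up a little power. In Aims 2 and 3 the direction is less comfortable. The study's hypotheses are supported when an interval includes zero, so an avoidably wide interval makes it easier to miss a real difference and call the arms comparable.

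Two smaller wording points belong to the same text. Change is planned for subjective effects of vaping, a measure many participants may hardly be able to answer at week 0. The contingent models are called logistic although the measures they are to explain are described as quantitative.

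**Working it through.** **1. Are the strata used anywhere?** Aims 1 to 4 in Section II.C name neither race nor gender in any between-group comparison. Gender appears once in each list of candidate factors for the contingent regressions of Aims 2 and 3; race is not listed by name. Those models look for reasons behind a difference already found and do not estimate the arm effect.

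**2. The plan's power.** Inputs from Section II.C: 400 per arm, 73% in the menthol arm, margin 0.09, one-sided error 2.5%. The true rate is taken as 73% in both arms.

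- Power = Φ(0.09/SE − 1.96), with SE = √(2v/400)
- v = 0.73 × 0.27 = 0.1971, so SE = 0.03139
- 0.09/0.03139 = 2.867, and Φ(0.907) = 81.8%, which reproduces the stated 82%
- 95% half-width = 1.96 × 0.03139 = 6.15 points

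**3. Aim 1 with stratification.** The adjusted v is the weighted within-stratum p(1 − p). The documents give no switching rate by race or gender, so the gaps below are assumptions, each keeping the overall rate at 73%. The 80/20 split echoes the statement in Section I.B, "We anticipate enrolling > 80% racial/ethnic minorities (primarily AA and Latinx) into the current study"; the 50/50 split could represent gender. For the first row, v = 0.8 × 0.75 × 0.25 + 0.2 × 0.65 × 0.35 = 0.1955.

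| Split | Assumed rates | v | SE | Half-width (points) | Power |
|---|---|---|---|---|---|
| none | 0.73 | 0.1971 | 0.03139 | 6.15 | 81.8% |
| 80/20 | 0.75 / 0.65 | 0.1955 | 0.03126 | 6.13 | 82.1% |
| 80/20 | 0.77 / 0.57 | 0.1907 | 0.03088 | 6.05 | 83.0% |
| 50/50 | 0.78 / 0.68 | 0.1946 | 0.03119 | 6.11 | 82.3% |
| 50/50 | 0.83 / 0.63 | 0.1871 | 0.03059 | 6.00 | 83.7% |

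The gain is 0.3 to 1.9 points of power. In participants per arm it is worth 400 × (1 − 0.1955/0.1971) ≈ 3 to 400 × (1 − 0.1871/0.1971) ≈ 20.

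If the strata are forced into balance, the unadjusted analysis already benefits in part. Its power is Φ((0.09 − 0.06153)/SE of the adjusted estimate), which runs from 81.9% to 82.4%, so the gain is 0.2 to 1.3 points. No blocking is described, so balance within strata is not assured.

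**4. Is the gain bought with type I error?** In simulation (four strata, gaps of 10 to 20 points, with and without forced balance, 200,000 runs per scenario), one-sided error at the margin was 2.5–2.6% for Mantel-Haenszel and 2.2–2.5% unadjusted. Power was 82.2–84.0% against 81.9–82.6%. With no gap the two were practically the same (81.8–81.9% against 81.7–81.8%). The planned interval is therefore nominal or slightly conservative, and the stratified one holds its level.

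**5. Aims 2 and 3: change score against ANCOVA.** Let r be the correlation between baseline and week 12, and k the week-12 SD divided by the baseline SD. The documents give neither, so both are assumed.

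- Variance per participant, in baseline-SD² units: change score 1 + k² − 2rk; ANCOVA k²(1 − r²)
- Half-width = 1.96 × √(2 × variance/400)
- Width ratio = √[(1 + k² − 2rk) / (k²(1 − r²))], which at k = 1 is √(2/(1 + r))

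With k = 1:

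| r | Half-width, change (SD) | Half-width, ANCOVA (SD) | Excess width |
|---|---|---|---|
| 0.3 | 0.164 | 0.132 | 24% |
| 0.5 | 0.139 | 0.120 | 15% |
| 0.7 | 0.107 | 0.099 | 8.5% |
| 0.9 | 0.062 | 0.060 | 2.6% |

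For r from 0.3 to 0.7, the excess is 43–55% at k = 0.7 and 0.5–11% at k = 1.3. E-liquid grams have no baseline value, so only adjustment for strata applies there.

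**6. What this does to the reading of comparability.** Take an assumed true difference of 0.2 SD, with k = 1. The chance that the interval still contains zero is Φ(1.96 − 0.2/SE). At r = 0.5 the change-score SE is √(2 × 1/400) = 0.0707, giving 19%; the ANCOVA SE is √(2 × 0.75/400) = 0.0612, giving 10%. At r = 0.3 the figures are 33% and 16%, and at r = 0.7 they are 4.5% and 2.3%.

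**7. The two wording points.** (a) Section V.B gives the subjective-effects scale at all time points, and Aim 3 analyses its mean change. The eligibility table in Section II.D excludes people who vaped on four or more of the previous 30 days. Many may thus have little recent vaping to rate at week 0, though the documents do not report prior EC experience. (b) Aims 2 and 3 describe the measures as quantitative, name logistic regression for the contingent models, and define no binary outcome.

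**The case against.** The unadjusted interval estimates exactly the P1 − P2 on which the hypotheses, margin and power rest, and it is valid. The Aim 1 gain is at most about two points of power under assumed gaps, and at most 1.2 in the 80/20 case. A change score is a legitimate use of baseline, and Hypothesis 2 is itself stated as change. The size of the loss in Aims 2 and 3 depends wholly on assumed correlations and SDs, and is only 2.6% at r = 0.9 with equal SDs. The deeper weakness there is reading an interval containing zero as comparability without a margin, which ANCOVA does not cure. Aim 3 does not name the reference visit for its change scores; week 0 is only the natural reading.

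Much of this stands as qualification. The Aim 1 gain is small, the Aims 2 and 3 figures are ranges rather than estimates, and the zero-in-interval rule stays in place. None of it is a reason to keep the wider interval. In large samples ANCOVA is no less precise than the change score at any r or k, and with equal SDs it estimates the same arm effect under randomization as with unequal ones. Narrower intervals reduce the risk that the reading rule creates, even though they do not remove it.

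**Conclusion.** The point holds as a matter of efficiency. It is not a matter of bias or false-positive risk.

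- **Aim 1:** the planned interval is sound. Stratifying would add 0.3 to 1.9 points of power under assumed 10- to 20-point gaps (0.2 to 1.3 if strata are balanced), and nothing meaningful if race and gender do not predict switching.
- **Aims 2 and 3:** this is where the change is worth most. Change-score intervals are 8.5% to 24% wider than necessary at r = 0.7 to 0.3 with equal SDs, less at higher r, and anywhere from 0.5% to 55% wider over the unequal SDs considered. All of these rest on assumed correlations and SDs.
- **Wording:** the subjective-effects comparison is poorly defined at its starting point, and the contingent models have no stated outcome.

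The change should be made, because it costs nothing and the extra width in Aims 2 and 3 leans towards the study's own hypotheses.

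**What to change.** - **Aims 1 and 4:** report a risk difference stratified by race and gender with its 95% interval, compared with -0.09 for Aim 1. Name one estimator in advance (Mantel-Haenszel or standardized), and define the race categories used as strata, which the documents do not do.
- **Aims 2 and 3:** use ANCOVA of the week-12 value on arm, baseline value, race and gender. For e-liquid grams, adjust for race and gender only.
- **Subjective effects of vaping:** compare week-12 scores between arms, adjusted for the strata, in place of change from week 0.
- **Contingent explanatory models:** state the dependent variable, and use linear regression where it is a quantitative measure.

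The cost is analysis-plan wording only. Race, gender and the baseline values are already part of the design, and no new data, visits or participants are needed. The wording should be settled before outcome data are examined, since covariates chosen afterwards are open to challenge.

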
The objective of this application is to provide much needed data to the FDA to guide regulatory action on EC flavoring. Menthol smokers (n=800), stratified by race and gender, will be randomized 1:1 into a 12-week open label, non-inferiority trial comparing a 4th generation nicotine salt-based pod-system EC in menthol- versus tobacco-flavored e-liquid. Follow-up will continue through week 26. The central hypothesis is that tobacco EC are not inferior to menthol EC at facilitating a switch to EC in menthol cigarette smokers.

Our specific aims are:

- 1) Compare the effectiveness of menthol versus tobacco EC at facilitating switching at week
  - **12.** Hypothesis 1: Participants randomized to tobacco EC (versus menthol EC) will demonstrate non-inferior rates of complete and predominant switching to EC (primary outcome). Complete switching is defined as exclusive use of EC, confirmed with CO < 6 ppm, and predominant switching is defined as use of EC with > 50% reduction in CPD. Rates of complete and predominant switching will also be compared separately by group.

- 2) Compare tobacco harm reduction of menthol versus tobacco EC at week 12. Participants randomized to tobacco EC (versus menthol EC) will demonstrate comparable (i.e., no statistically significant differences) change in CO, respiratory symptoms, lung function, blood pressure, and tobacco-related quality of life from baseline to week 12.
- 3) Compare the acceptability of menthol versus tobacco EC at week 12. Hypothesis 3: Participants randomized to tobacco EC (versus menthol EC) will consume comparable amounts of study provided e-liquid (measured in grams) and demonstrate comparable reductions in cigaretterelated withdrawal, craving, and dependence. Subjective effects of vaping will also be compared between groups.
- **4) Examine the long-term effectiveness of menthol versus tobacco EC at week 26.** Switching patterns at week 26 will be compared to examine long-term maintenance of EC and smoking patterns under naturalistic conditions (EC only provided up to week 12). Hypothesis 4: There will be no statistically significant difference in rates of complete or predominant switching at week 26 between those randomized to menthol versus tobacco EC.

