#### **B. Outcome**

#### EFFECTIVENESS (Aims 1 & 4).

Switching (Primary Outcome). The primary outcome is the proportion of menthol smokers who make a complete or predominant switch to EC, defined as use of EC along with a > 50% reduction in cigarettes from baseline to week 12. The 7-day Timeline Follow Back Interview (TLFB) will be used to assess participants cigarette and EC use patterns each day for the past 7 days at each visit (weeks 0, 4, 8, 12, 18, 26). The primary endpoint is, however, fixed at week 12. The TLFB is a reliable and valid way of collecting information about substance use quantity and frequency and, in tobacco research, has been corroborated against interactive voice response, butt counts (storing and returning the butts of cigarettes smoked), and biological measures for cigarettes smoked and puff topography for EC, supporting the strong validity of this self-report measure compared to other 'gold standard' measures. For each of the last 7 days participants will be asked to recall the number of cigarettes smoked and EC sessions vaped; following standard practice, an EC session is defined as at least 15 puffs or lasting around 10 minutes. For each EC session, participants will be asked to specify the device used (i.e., study provided versus something else) and the flavor (i.e., menthol, Virginia tobacco, something else).\* For non-study provided EC, detailed information will be collected about the type of EC (e.g., brand, podbased, disposable, refillable), flavor, nicotine concentration and, if available, whether the product is nicotine salt-based. To aid in recall and corroborate self-report, participants will be given dated bags to collect all EC. Bags will be returned at each visit during the intervention phase and used to confirm use of study provided EC (i.e., grams of e-liquid consumed) and protocol adherence (i.e., the number of pods vaped in the study provided versus non-study provided flavor). *Complete switching* is defined as any use of EC and no use of cigarettes in the past 7 days (i.e., 100% reduction in CPD from baseline), biochemically confirmed with an expired breath CO < 6 parts per million (ppm). CO is used for verification because cigarettes produce carbon monoxide as a byproduct of combustion, while heating an e-liquid does not generate CO. The < 6 ppm CO cutoff is more conservative than the  $\leq$  10 ppm cutoff that is commonly used and reflects the current state of knowledge for detecting recent cigarette smoking. Predominant switching is defined as those who report any use of EC along with a > 50%reduction from baseline in CPD. A > 50% reduction has been selected because it is a measure of acceptability of the EC products and is associated with substantial reductions in biomarkers of harm and exposure relative to continued smoking and is a common endpoint used in tobacco harm reduction studies. Partial switching will be defined as those who report any use of EC along with a  $\leq$  50% reduction from baseline in CPD. No switching (i.e., exclusive cigarette user) will be defined as those who reported no use of ECs and any use of cigarettes in the past 7 days. A potential fourth group, no use of e-cigarettes or combustible cigarettes, may occur. For all switching trajectories, use of EC will be corroborated with pod counts and objectively measured EC pod weights during the intervention phase.

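### Hypotheses 2 and 4 treat a non-significant difference as the sign of similarity, with no margin; a true 9-point week-26 deficit would meet Hypothesis 4 about 21% of the time at the plan's week-12 rates

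*Combined protocol and SAP*

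**What the plan says.** Hypothesis 4 (section I.A, and section II.C under Aim 4) is itself a statement of non-significance: "There will be no statistically significant difference in rates of complete or predominant switching at week 26". The Aim 4 analysis calculates the switching proportions and a 95% confidence interval for their difference, and gives no rule for reading that interval. Two versions are planned: one counts those lost as non-switchers, and the plan will "subsequently report on completers only". On attrition it says: "We do not expect the lost to follow-up rate to exceed 20% at month 6".

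Hypothesis 2 (sections I.A and II.C, Aim 2) says that the tobacco EC group "will demonstrate comparable (i.e., no statistically significant differences) change in CO" and the other harm-reduction measures. Aim 3 does not define the term this way but carries the same expectation for its comparisons: "This means that we expect to fail to reject each of the t-tests", with each interval containing zero.

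The only margin, -0.09, is set in section II.C for the week-12 primary outcome, and section V.B says of that outcome: "The primary endpoint is, however, fixed at week 12". Under Aim 1, the separate comparisons of complete and of predominant switching carry a caveat: "we have not specified an a priori difference threshold for these analyses and, therefore, they are not testing noninferiority and should be considered exploratory". Hypotheses 2 and 4 carry no such caveat.

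**The concern.** Failing to find a difference is not evidence that the difference is small. A criterion of non-significance also becomes easier to meet as the data become less precise, so attrition and noise favour the conclusion the investigators expect. The plan accepts this principle under Aim 1, where comparisons without a threshold are labelled exploratory, but does not apply it to Hypotheses 2 and 4, which also have no threshold.

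The stated objective (section I.A) is to inform FDA regulatory action on EC flavoring, and week 26 is the look at switching after the study supply has ended. A report that Hypothesis 4 was supported could be read as evidence that tobacco flavor holds up in the longer term, when the data might be compatible with a deficit larger than the one the plan rules out at week 12.

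**Working it through.** **Inputs.** From section II.C: 400 per arm; menthol rate 0.73 and tobacco rate at the margin 0.64, both for week 12; margin 0.09; type 1 error 2.5%; stated power 82%; loss at month 6 not expected to exceed 20%. Assumed: the week-26 rates, because none is given. The benchmark is a true deficit equal to the week-12 margin.

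**The plan's own figure.** Power at true equality is Φ(0.09/SE − 1.96), with SE = √(2 × 0.73 × 0.27/400) = 0.0314. This gives Φ(0.907) = 81.8%, which reproduces the stated 82%.

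**Chance that a true 9-point deficit is non-significant.** The 95% interval contains zero with probability Φ(1.96 − d/SE) − Φ(−1.96 − d/SE), where SE is unpooled. For 0.73 vs 0.64 and 400 per arm, SE = √((0.73 × 0.27 + 0.64 × 0.36)/400) = 0.0327 and d/SE = 2.75, so the probability is Φ(−0.79) = 21.4%. A pooled test gives 21.7% and exact binomial enumeration 21.4–21.5%.

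For other assumed menthol rates with the same 9-point deficit, and for completers only at the 20% ceiling (400 × 0.8 = 320 per arm):

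| Menthol / tobacco rate | 400 per arm | 320 per arm |
|---|---|---|
| 30% / 21% | 16% | 25% |
| 40% / 31% | 24% | 33% |
| 50% / 41% | 27% | 37% |
| 60% / 51% | 27% | 37% |
| 73% / 64% | 21% | 31% |

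**Those lost counted as non-switchers.** Start from 73% vs 64% with 400 per arm, and assume that loss is unrelated to switching within an arm. Each rate is multiplied by the proportion retained; for 20% equal loss, 0.73 × 0.8 = 0.584 and 0.64 × 0.8 = 0.512, so d = 0.072. The last column is the chance that the lower limit exceeds −0.09, Φ((0.09 − d)/SE − 1.96), in the same imputed data.

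| Loss, menthol / tobacco | Imputed rates | Non-significant | Lower limit above −0.09 |
|---|---|---|---|
| none | 0.730 / 0.640 | 21% | 2.5% |
| 10% / 10% | 0.657 / 0.576 | 34% | 4.5% |
| 20% / 20% | 0.584 / 0.512 | 46% | 7.4% |
| 10% / 15% | 0.657 / 0.544 | 9% | 0.4% |
| 15% / 10% | 0.6205 / 0.576 | 75% | 26% |

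Simulation of the non-significance column (400,000 trials) agrees to within 0.2 points. If those lost truly are non-switchers, there is no dilution.

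**What could be observed.** With an observed menthol rate of 73%, 400 per arm and no loss, the largest non-significant deficit solves d = 1.96 × SE(0.73, 0.73 − d), giving d = 0.0635. The lower limit is then −0.127 and the upper limit about zero. At week 12 the Aim 1 rule would call that result inconclusive; at week 26 it satisfies Hypothesis 4.

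**Hypothesis 2 and Aim 3.** The documents give no SDs or thresholds for these measures, so no corresponding figure can be calculated. This part rests on the wording alone.

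**The case against.** The best defence is that the consequence is inferred. Aim 4 plans estimation: proportions, a 95% interval and two treatments of loss. Hypothesis 4 is a prediction placed before that analysis, and the plan never says that non-significance proves similarity. In Aims 2 and 3 the only action tied to a test result is a follow-up regression when a difference is found. These are not primary aims, and a reader given the week-26 interval can compare it with −0.09.

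All of that is true, and it limits the point to what may be claimed from secondary analyses. It does not remove it. A hypothesis worded as non-significance tells the reader to check whether the interval contains zero, not how large a deficit it allows, and the Aim 1 caveat is missing where it is equally needed.

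Two objections to the numbers also stand in part. The 21% uses week-12 rates and no loss, so it illustrates the problem and does not forecast week 26. The 9%-to-75% spread comes from assumed unequal loss that the documents do not suggest. Further, 9 points is a generous benchmark at low rates: at a 40% menthol rate it is a ratio of 0.31/0.40 = 78%, below the 80% criterion cited in section II.C. What holds across the equal-loss scenarios is that the chance is far from negligible.

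**Conclusion.** The concern holds. As worded, Hypothesis 4 can be met by a tobacco EC group that is truly 9 points worse. The chance is about 21% at 73% vs 64% with 400 per arm and no loss, 16% to 27% for menthol rates of 30% to 73%, and 25% to 37% with 320 completers per arm. With those lost counted as non-switchers, it depends on the loss pattern and can move either way. All of these rest on assumed week-26 rates and on using the week-12 margin as the benchmark. Hypothesis 2 and the Aim 3 expectation share the flaw in reasoning, without a size. The week-12 primary analysis is not affected. This should be corrected, but it does not threaten the trial's main conclusion.

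**What to change.** **Hypothesis 4.** Before outcome data are examined, choose one of two routes.

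- Claim week-26 non-inferiority only if the lower 95% limit for tobacco minus menthol exceeds a pre-stated, justified margin. Name which of the two planned analyses decides, show the other beside it, and note that counting those lost as non-switchers can dilute this test too. The margin must be argued at the expected week-26 rate: −0.09 is an effectiveness ratio of 88% at a 73% menthol rate, 82% at 50% and 78% at 40%, and it falls below the plan's own 80% criterion under a 45% rate (0.36/0.45 = 80%).
- Or report the estimate and 95% interval, make no similarity claim, and extend the Aim 1 exploratory caveat to week 26.

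**Aims 2 and 3.** Remove the definition of comparable as non-significant and the reading based on whether the interval contains zero. Report estimates with 95% intervals and draw no conclusion of comparability.

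**Cost.** Wording only, with no new data. The first route makes the week-26 claim harder to earn: with −0.09, power at true equality is 72–82% at 400 per arm and 62–73% with 320 completers per arm, for menthol rates of 30–73%. Carrying the plan's 88% ratio to lower rates, with margin = rate × (1 − 0.64/0.73), gives 7.4 points at 60% (power 57% at 400 per arm), 6.2 at 50% (41%) and 4.9 at 40% (30%). The second route has no power cost.
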